3.8.1 Major protocol violations

A major protocol violation will be defined as:

- Restrictive O₂ group: during the intervention period
 - For non-intubated trial participants: Supplemental oxygen ≥ 3 L O₂/min and having an SpO₂ $\geq 98\%$ recorded in two consecutive hourly values in the data collection sheet: "Randomisation, data collection sheet and REDCap inclusion"
 - For intubated trial participants: FiO₂ ≥ 0.4 and having an SpO₂ $\geq 98\%$ recorded in two consecutive hourly values in the data collection sheet: "Randomisation, data collection sheet and REDCap inclusion"

- Liberal O₂ group: during the intervention period
 - For non-intubated trial participants: Supplemental oxygen <3 L O₂/min in two consecutive hourly values in the data collection sheet: “Randomisation, data collection sheet and REDCap inclusion”
 - For intubated trial participants: FiO₂ <0.4 in two consecutive hourly values in the data collection sheet: “Randomisation, data collection sheet and REDCap inclusion”

4. Drug management and accounting

4.1 Drug management

The investigated drug will be handled by the usual providers: Air Liquide A/S, Strandmøllen A/S and Linde Gas A/S.

4.2 Drug accounting

As the consumption of the trial medicine, oxygen, is continuous in all prehospital and intrahospital units, the providers (Strandmøllen A/S, Linde Gas A/S and Air Liquide A/S) will register batch numbers and expiration dates as usual. Detailed accounting and registration of the drugs will not be possible, as oxygen runs through central pipelines and thus cannot be tracked on an individual trial participant level. However, we foresee no possible complications or risks beyond the existing, which will be entirely unrelated to this study. Any potential problems with the delivery will not affect the enrolled trial participants any further than it would were they not enrolled in the study. No other methods to study oxygen at our institution are possible. Therefore, appendix 12 (“Produktresuméer for oxygen ved Air Liquide, Strandmøllen og Linde Gas, kryogen og komprimeret”) will be the most detailed available source of drug accounting and thus serve as the primary source.

5. Safety management

5.1 Definitions

The following definitions will be used²⁶:

- Adverse Event (AE): Any untoward medical occurrence in a subject to whom a medicinal product is administered and which does not necessarily have a causal relationship with this treatment.
- Serious Adverse Event (SAE): Any untoward medical occurrence that at any dose requires inpatient hospitalisation or prolongation of existing hospitalisation, results in persistent or significant disability or incapacity, results in a congenital anomaly or birth defect, is life-threatening, or results in death.
- Suspected Unexpected Serious Adverse Reaction (SUSAR): A suspected, serious adverse reaction, the nature, severity or outcome of which is not consistent with the reference safety information.

5.2 Tracking of events

The local investigators at each centre is responsible for recording the different types of AEs and SAEs in the trial participant's Case Report Form in REDCap. The specific investigator will assess the correlation between an event and trial medicine using the following AE/SAE event policy:

- 1: Unrelated – No temporal context; other etiologies are more likely to be the cause
- 2: Possible related – Less clear connection; other etiologies are also possible
- 3: Probably related – Clear temporal correlation with medication discontinuation, and not reasonably explained by the known clinical condition of the subject
- 4: Related – Clear temporal relationship with rehabilitation test or clinical assessment

To monitor AEs and SAEs, a TRAUMOX2 investigator will assess the trial participant's medical record:

- Once within the first 24 hours
- Every third day until discharge (maximum of 30 days)

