5.3 Adverse Events and Serious Adverse Events

This group of trial participants are expected to have a lot of complications. It is the established practice in trials on critically ill patients that adverse events are part of the natural trajectory of the primary disease process or expected complications of the critical illness.²⁷

Therefore, we have chosen to record only the following AEs:

- Atelectasis
- Irritability of airway mucosa

We will register all SAEs. The registration will be done in REDCap and once a SAE registration is complete, the sponsor and coordinating investigator will receive an e-mail notification within 24 hours via the REDCap notification e-mail system. Thus, the law on immediate notifying (within 24 hours after it has come to an investigator's knowledge) the sponsor about SAEs is being followed.

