Oxygen is a well-known drug given in a dosage of FiO_2 0.21-1.0 and can be administered by paramedics, nurses, and doctors. The side-effects of normobaric oxygen-strategies include slightly decreased heart rate as well as increased risk of atelectasis, pleuritis and respiratory distress syndrome. The greater the FiO_2 , the greater the risk. As the standard treatment of care currently includes high levels of FiO_2 , it seems plausible that the intervention group will have a decreased risk for developing these side-effects. On the other side, hypoxia is documented to be deleterious. To avoid the risk of hypoxia, all trial participants will be monitored with continuous pulse oximetry and arterial blood gases to avoid desaturation. If the saturation is unmeasurable due to e.g. hypovolemia or hypothermia the treating physician will decide and document the treatment of choice. When measurable again, the allocated intervention will resume. In the TRAUMOX1 trial, we observed only seven episodes of desaturation (SpO_2 below 90%) in the restrictive group (median 87% [87-89]). Of note, five of the seven cases of SpO_2 below 89% occurred in two trial participants; one trial participant who had just been extubated and another trial participant who went into cardiac arrest for another reason than hypoxemia.

The trial participants receiving the standard treatment and what is recommended in current guidelines (liberal oxygen) will not be put at any additional risk compared to trial participants not enrolled in the study. However, we suspect this standard treatment is not always beneficial. As outlined in the background section, we hypothesise that a liberal supplemental oxygen strategy may be detrimental and should be avoided as soon as possible. Thus, the restrictive supplemental oxygen (intervention group) may be associated with fewer side effects, with no additional risk, as seen in other trial participant populations. Therefore, we believe that this study may be beneficial for the single trial participant. Finally, there will be no risk of delaying treatment due to enrolment, as the treating physician will be treating the trial participant as usual, until the randomisation results are available, and the allocation has begun. Therefore, we think that the study will add no risk for the included trial participants.

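### The AE/SAE causality scale has no usable criterion for its two upper grades in an eight-hour oxygen-strategy trial, and it grades relation to oxygen rather than to the allocated strategy

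*Protocol*

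**What the plan says.** The grading rule is in Protocol section 5.2: "The specific investigator will assess the correlation between an event and trial medicine using the following AE/SAE event policy". Section 4.2 identifies the medicine in passing: "the consumption of the trial medicine, oxygen, is continuous in all prehospital and intrahospital units". The four grades run from Unrelated to Related. The three that allow a relation are worded as follows:

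- Grade 2, Possible: "Less clear connection; other etiologies are also possible".
- Grade 3, Probably: "Clear temporal correlation with medication discontinuation, and not reasonably explained by the known clinical condition of the subject".
- Grade 4, Related: "Clear temporal relationship with rehabilitation test or clinical assessment".

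Section 5.3 limits recorded AEs to two, atelectasis and "Irritability of airway mucosa", and then commits to registering every SAE. Section 5.1 defines a SUSAR through the word suspected, and section 5.4 sends all potential SUSARs to the sponsor. Neither section mentions a causality grade. Hypoxaemia during the intervention (saturation below 90%) is a secondary outcome in section 3.6.2. Myocardial infarction and cerebral ischaemia are among the data points in section 3.7. SAP section 5.4.1, which covers the biomarker sub-study, refers back to the main trial's event registration and offers no other scale.

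**The concern.** A causality scale works when each grade tells the investigator which exposure to look at and what timing counts. Here the exposure is a fixed eight-hour period of one of two oxygen strategies. An event that a clinician would suspect begins during that period or in the hours or days after it, and it may come from too much oxygen or too little. Section 6.1 itself describes hypoxia as harmful. The two upper grades describe neither that timing nor the restrictive direction.

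What is at stake is the consistency of safety grading across centres in several countries, and the handling of a serious event that might be a suspected reaction. There is also a reporting issue: the short AE list contains nothing that represents under-oxygenation, so the AE tabulation alone would give a partial picture of harm by arm.

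**Working it through.** The plan states no figure on this point, so the check is textual: what each grade requires, set against what this trial can supply.

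| Grade | Anchor in section 5.2 | Does it describe onset during or after the allocated strategy? |
|---|---|---|
| 1 Unrelated | No link in time; another cause more likely | No, and rightly so |
| 2 Possible | A weaker link; other causes also possible | Usable for any event, but worded for an unclear link |
| 3 Probably | Timing of medication discontinuation | Only if the end of the period, or lowering oxygen, is read as discontinuation |
| 4 Related | Timing of a rehabilitation test or a clinical assessment | No. The first has no referent in the documents; the second is not an exposure |

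Four typical events can then be passed through the scale.

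1. *Serious event starting within the eight hours of liberal oxygen, with a clear link in time.* Grade 1 does not fit, because there is a link. Grade 2 understates a clear link. Grade 3 requires a link to stopping, which has not happened. Grade 4 is reachable only by treating clinical assessment as if it meant exposure to oxygen.
2. *Serious respiratory event some days later.* The eight-hour period has ended, so some investigators may read that end as discontinuation and choose grade 3. Others will choose grade 2. The text supports either.
3. *Serious hypoxic event under the restrictive strategy.* It is registered as an SAE. The question put to the investigator is its relation to oxygen, whereas the suspected cause is having less of it. Some may count reduced oxygen as discontinuation, while others may judge that the medicine did not cause the event.
4. *Non-serious desaturation under the restrictive strategy.* It is neither an SAE nor one of the two listed AEs, so it receives no causality grade. It is counted under the hypoxaemia outcome.

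Two further points follow from reading the sections together.

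- *SUSAR threshold.* Sections 5.1, 5.2 and 5.4 do not say which of grades 2, 3 and 4 make a reaction suspected.
- *Ischaemic events.* Section 3.7 collects them. They are not in the outcomes of sections 3.6.1 and 3.6.2, nor in the AE list of section 5.3. One that meets the SAE definition is registered as an SAE; otherwise no section says where it will be reported.

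Other routes do not fill the grading gap. Under section 6.4 the DMSC receives a yearly overall SAE number, and interim files with death, pneumonia and ARDS by group code. It may request extra reviews, but SAEs, hypoxaemia and ischaemic events by arm are not part of the routine supply.

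**The case against.** The strongest reply is that little is lost. All SAEs are registered whatever their type or arm. Grade 2 is open to any event, and grade 4 offers clinical assessment as an alternative, which does take place in this trial. Hypoxaemia, mortality, pneumonia and ARDS are compared between arms without any causality judgement. No section makes SUSAR reporting depend on grade 3 or 4, and no primary or secondary analysis uses the grades. All of this stands, and it limits the point to grading and reporting.

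Several stronger readings are tempting but are not supported.

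- *That harm from restricting oxygen cannot be graded as related.* It can, by way of clinical assessment or a broad reading of discontinuation. What is missing is a clear criterion.
- *That restrictive participants breathing room air fall outside the AE definition*, which speaks of "Any untoward medical occurrence in a subject to whom a medicinal product is administered". Sections 3.5.1 and 6.1 treat 21% oxygen as a dose, and the SAE definition applies at any dose.
- *That both listed AEs are documented effects of high oxygen.* Section 6.1 names "slightly decreased heart rate as well as increased risk of atelectasis, pleuritis and respiratory distress syndrome" and says risk rises with the inspired fraction. That covers atelectasis but does not mention mucosal irritability.
- *That every participant in the restrictive arm is affected.* Grading concerns only those with a recorded event, and the documents do not say how many that will be.

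Nor is there a case for rewriting the section 5.1 definitions, which cite the EU regulation, or for lengthening the AE list, whose brevity section 5.3 explains with a reference on trials in the critically ill.

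**Conclusion.** The concern holds as a defect in an operative safety rule. Two of the four grades, the upper two, have no usable criterion for an eight-hour oxygen strategy in either arm, and the question put to the investigator is about oxygen rather than about the strategy being tested. Serious harm is captured and can be graded, but the grade is likely to vary between centres. Non-serious harm from restriction is counted through the hypoxaemia outcome without a causality grade, and ischaemic events have no stated place in the reporting.

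The documents give no basis for putting a number of participants or misgraded events on this. That grading will be inconsistent is an inference from the wording, not an observed fact. The odd phrase in grade 4 may be a translation or copying slip for a re-exposure test. That is an assumption, and it would not rescue the criterion, because the protocol describes a single eight-hour period with no planned re-exposure. The efficacy conclusions are untouched.

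**What to change.** In Protocol section 5.2:

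- Reword the stem so that the investigator grades relation to the allocated oxygen strategy, whether through giving or restricting oxygen.
- Reword grades 3 and 4 as a clear temporal relation to that strategy, with plausible onset during or after the eight-hour period. Keep the existing idea that the participant's known condition does not reasonably explain the event, and say what separates grade 4 from grade 3.
- State which grades count as a suspected reaction for SUSAR assessment.

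In the safety reporting, present hypoxaemia episodes and ischaemic events by arm in the same place as the AEs and SAEs. Both are already collected, so this needs no new data and remains possible late in the trial. If the wording changes while the trial is running, identify events graded before and after the change.

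The cost is minor protocol and eCRF wording, and probably somewhat more events graded as possibly related.

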3.2 Inclusion criteria

- Patients aged ≥ 18 years, including fertile women*
- Blunt or penetrating trauma mechanism
- Direct transfer from the scene of accident to one of the participating trauma centres
- Trauma team activation
- The enrolling physician must initially expect a hospital length of stay for 24 hours or longer

**There is no added risk for enrolment of fertile women as oxygen administration is approved for this group of patients*

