	
FiO₂: Lowest value ensuring a saturation = 94%
 
Only trial participants receiving an FiO₂ = 0.21 can saturate >94%
 
Pre-oxygenation as usual prior to intubation
	
After intubation: Ventilator
 
FiO₂: Lowest value ensuring a saturation = 94%
 
Only trial participants receiving an FiO₂ = 0.21 can saturate >94%
	
FiO₂ can be reduced to ≥0.6 if the arterial oxygen saturation is ≥98%
	
After intubation: Ventilator
 
FiO₂ can be reduced to ≥0.6 if the arterial oxygen saturation is ≥98%

ICU or PACU or ward
	
Connected to ventilator
 
FiO₂: Lowest value ensuring a saturation = 94%
 
Only trial participants receiving an FiO₂ = 0.21 can saturate >94%
 
Pre-oxygenation as usual prior to intubation
	
No supplemental oxygen/nasal cannula/non-rebreather mask depending on the saturation
 
If saturation is <94%: Lowest O₂ flow (between 0-15 L/min) ensuring a saturation = 94%
 
Only trial participants receiving no supplemental oxygen can saturate >94%
	
Connected to ventilator
 
FiO₂ can be reduced to ≥0.6 if the arterial oxygen saturation is ≥98%
	
A non-rebreather mask
 
O₂ flow can be reduced to ≥12 L/min if the arterial oxygen saturation is ≥98%

The duration of the intervention is eight hours.

All trial participants will have two arterial blood gasses (ABGs) drawn within the intervention period in order to adjust supplemental oxygen treatment according to allocation.

The 1st ABG will be drawn at **hour 1 ± 30 minutes (T1)** after randomisation (initiation of intervention is considered hour 0). If an ABG is not obtainable at T1 due to still being pre-hospital or other circumstances, the ABG must be obtained as soon as possible.

The 2nd ABG will be drawn at **hour 6 ± 2 hours (T6)** after randomisation.

**In case non-intubated trial participants require intubation, this is done and the study is continued for intubated trial participants in the same arm.*

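### Scheduled AE/SAE review can precede the end of the 8-hour intervention and stops at discharge, and the SAE alert runs from form completion rather than from knowledge, so some events may be missed or reported late

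*Protocol*

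**What the plan says.** Protocol section 5.2 (repeated in the synopsis row on tracking of events) begins with a general duty: local investigators are "responsible for recording the different types of AEs and SAEs in the trial participant's Case Report Form in REDCap". It then gives the working schedule: "To monitor AEs and SAEs, a TRAUMOX2 investigator will assess the trial participant's medical record", namely "Once within the first 24 hours" and "Every third day until discharge (maximum of 30 days".

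Four other places bear on this:

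- Section 3.5.3: "The duration of the intervention is eight hours".
- Section 3.2: "The enrolling physician must initially expect a hospital length of stay for 24 hours or longer". This is an expectation at enrolment, not an observed minimum.
- Section 5.1 defines an SAE as "Any untoward medical occurrence that at any dose requires inpatient hospitalisation or prolongation of existing hospitalisation", followed by the disability, congenital, life-threatening and fatal criteria. Section 5.3 undertakes to register every SAE.
- Section 5.3 on notification: "once a SAE registration is complete, the sponsor and coordinating investigator will receive an e-mail notification within 24 hours". It concludes from this that the legal limit, 24 hours from the investigator's knowledge, is met.

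The SAP (section 5.4.1) refers back to the main trial for harms and adds no schedule.

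**The concern.** Three features of the text do not fit what it sets out to do.

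1. **The only review can come too early.** The first review may be done while oxygen is still being given under allocation. A later review would read back over that time, but a participant discharged before it falls due has none.
2. **The schedule ends at discharge.** The 30 days in section 5.2 are a cap, not a follow-up period. For someone already an inpatient, the hospitalisation criterion can be met by prolongation in hospital or by readmission later, and no stated step looks for readmission. A death after discharge would reach the primary outcome, but no step is stated for entering it as an SAE with a relatedness grade.
3. **The notification claim does not follow.** The e-mail is timed from a completed registration. No limit runs from knowledge to completion.

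At stake are the completeness and timeliness of the AE and SAE record. That includes the two AE terms the protocol chose to record, one of which (atelectasis) section 6.1 lists as an oxygen side effect. The yearly SAE total sent to the DMSC under section 6.4 draws on the same record. SAE observation time also depends on length of stay, which is itself a secondary outcome.

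**Working it through.** The plan states no figure on this point, so there is nothing to reproduce. The check is a timeline.

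**Inputs.** First review at hour t, with t between 0 and 24 (section 5.2). Next review 72 h later (section 5.2). Intervention from hour 0 to hour 8 (section 3.5.3). Discharge at hour L. Assumption: the first 24 hours are counted from the start of the intervention. The text does not say whether the three-day cycle runs from the first review or from hour 0, so both are shown where they differ.

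**Formulas.** Unread stay = L − (time of last review). Unread intervention = 8 − t if t is below 8 and no second review falls due, otherwise 0. Days from discharge to day 30 = 30 − L/24.

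**Part of the permitted window before the intervention ends.** 8/24 = 33%.

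| First review (h) | Discharge (h) | Second review | Unread stay (h) | Unread intervention (h) | Days to day 30 |
|---|---|---|---|---|---|
| 2 | 24 | none | 24 − 2 = 22 | 8 − 2 = 6 | 29.0 |
| 2 | 36 | none | 36 − 2 = 34 | 6 | 28.5 |
| 2 | 48 | none | 48 − 2 = 46 | 6 | 28.0 |
| 2 | 71 | none | 71 − 2 = 69 | 6 | 27.0 |
| 2 | 72 | none if cycle runs from first review; at 72 h if from hour 0 | 70 or 0 | 6 or 0 | 27.0 |
| 2 | 96 | at 74 h or 72 h | 22 or 24 | 0 | 26.0 |
| 24 | 48 | none | 48 − 24 = 24 | 0 | 28.0 |

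Two things follow. The gap over the intervention needs both conditions together, a first review before hour 8 and discharge before the second review. The gap at the end of the stay needs neither: even a first review at hour 24 leaves 24 h of a 48 h stay unread, and the stretch after discharge is always unscheduled.

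**Notification, side by side.** Section 5.3 claims: knowledge to sponsor within 24 h. Section 5.3 provides: knowledge to completed form, no limit; completed form to e-mail, within 24 h. The total has no upper bound. Section 5.4, by contrast, counts the SUSAR limit from discovery. Sections 5.3 and 5.4 therefore use different starting points.

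**The case against.** The best defence is that the schedule is a minimum laid over a general recording duty. On that reading events are not found by chart review alone, and no sentence says that a known readmission or post-discharge death falls outside the SAE definition. That stands. However, the duty names no route by which an investigator would learn of an event after discharge.

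Many important harms are also caught elsewhere. Section 3.6.2 lists mortality at 30 days and 12 months, pneumonia and ARDS within 30 days, surgical site infection within 30 days, and hypoxaemia during the intervention. Section 3.7 adds hourly saturation records. This also stands, with two limits: pneumonia after discharge is seen only where prescription data exist, and these outcome routes carry no relatedness grade or sponsor alert.

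A reader might be tempted further than the documents allow:

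- *Harms in short-stay participants are missed.* The text shows only that some may be. The alert trigger can delay notice but cannot make an event go unrecorded.
- *A third of participants are affected.* The 33% is a part of a time window. It would be the share of first reviews only if their timing were uniform, and it is not a share of participants.
- *The arms will differ in SAEs because one goes home earlier.* This is possible but hypothetical. SAE counts are not listed outcomes, the yearly DMSC figure is an overall total, and the suggested stopping guidance rests on 30-day mortality.
- *SUSAR reporting is compromised.* Section 5.4 counts from discovery, so the form-completion trigger does not govern it.

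Finally, the phrase about continuing until discharge could be read to include a look on the day of discharge. It is ambiguous, which is itself a reason to state it.

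**Conclusion.** The point holds as a limited gap in safety surveillance. Scheduled review can leave up to 8 h of intervention unread, in the extreme case of a review at hour 0 and discharge before the second review. It can leave nearly three days of stay unread before discharge, and everything from discharge to day 30. The SAE notification passage claims a limit counted from knowledge that its stated procedure does not secure, and the two statements must be reconciled.

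The consequence is that some AEs and SAEs may be missed or reported late. Those most exposed are non-fatal events after discharge such as readmission, the two recorded AE terms, and events late in a short stay. The number of participants affected cannot be computed, because the documents give neither a length-of-stay distribution nor the actual timing of first reviews. The hours above are illustrations at chosen review and discharge times, not estimates. The primary outcome and the SUSAR clock are not affected.

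**What to change.** In section 5.2 and the synopsis:

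- Time the first review after the 8-hour intervention has ended and still within 24 hours.
- Add a closing record review at discharge, covering everything since the last one. This brings the unread stay in the table to zero.
- Add an SAE check for readmission and death when the day-30 data are collected. The site investigator should do it, because section 3.4.1 keeps the outcome assessors blinded while SAE relatedness is judged against the trial medicine.
- State when the three-day cycle starts.

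In section 5.3:

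- Require a minimal SAE entry within 24 hours of the investigator's knowledge.
- Record the date and time of knowledge.
- Trigger the REDCap alert on first save instead of on completion.

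The cost is a wording amendment, a trigger setting, one extra chart look per participant at discharge, a few fields at day 30, and somewhat more SAEs to process. No treatment changes.
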